2.5.2 Other Safety Endpoints

2.5.2.1 Neonatal Morbidities

Neonatal morbidities at the end of treatment are defined in the eCRF as bronchopulmonary dysplasia, retinopathy of prematurity, intraventricular hemorrhage, periventricular leukomalacia, necrotizing enterocolitis, and late-onset sepsis.

Frequencies and percentages of premature infants born <37 weeks of gestation up to 1 month CA developing neonatal morbidities will be summarized descriptively by treatment group.

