6.3 Medical History and Prior Medications

Medical history information, including the diagnosis requiring PN, will be collected at Screening and updated as necessary at Baseline.

Diagnosis for requiring PN at Screening will be recorded (e.g. prematurity; congenital gastrointestinal malformation; gastrointestinal obstruction diseases; inherited gastrointestinal dysfunction and motility disorders; necrotizing enterocolitis; sepsis; short bowel syndrome, enteropathies including inflammatory gastrointestinal diseases; other gastrointestinal dysfunctions to be specified).

Medications and nutrition supplements received within 30 days prior to randomization, by the patient and the nursing mother (if applicable) also will be recorded at Screening. The nursing mother's medication history will be collected from the patient's chart (if available). There are no restrictions for prior medications.

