7.2.3 Standard-of-Care Procedures

The following procedures will be performed at intervals determined by the SOC at each investigational site (refer to Appendix 1, Schedule of Events Table):

- Laboratory evaluations including:
 - hematology complete blood count
 - chemistry basic metabolic panel and electrolytes
- Diagnosis of neonatal morbidities including bronchopulmonary dysplasia (BPD), retinopathy of prematurity (ROP), intraventricular hemorrhage (IVH), periventricular leukomalacia (PVL), necrotizing enterocolitis (NEC), and late-onset sepsis in enrolled premature infants born at 24 to <37 weeks of gestation up to 1 month CA with a birth weight ≥750g.

7.2.4 Days 15, 30, 45, 60, 75 and 90 or End of Study Treatment Procedures

The Study Treatment Period starts when the patient receives study treatment. End of study treatment is defined as the last day of PN with Intralipid or Clinolipid; maximum 90 days of study treatment is allowed.

The following procedures will be performed approximately every 15 days ± 2 days for patients continuing on PN (days 15, 30, 45, 60, 75 and 90) and within ± 2 days of the last day of study treatment (maximum 90 days on either Clinolipid or Intralipid) whenever that occurs:

- Physical examination including weight, length or height (and head circumference for infants <1 year of age)
- Vital signs
- Concomitant medications
- Concomitant procedures
- AEs
- Laboratory evaluations including:
 - Hematology parameters
 - Serum chemistry parameters
 - Hepatic integrity parameters
 - Total and direct bilirubin
 - Triglyceride levels
 - FA profile
 - Holman Index
 - Phytosterol, cholesterol, and squalene levels

In addition, the following data will be collected at end of study treatment:

 Diagnosis of neonatal morbidities including bronchopulmonary dysplasia (BPD), retinopathy of prematurity (ROP), intraventricular hemorrhage (IVH), periventricular leukomalacia (PVL), necrotizing enterocolitis (NEC), and lateonset sepsis in enrolled premature infants born <37 weeks of gestation up to 1 month CA.

After end of study treatment (maximum of 90 days), the patient will receive nutritional intervention as prescribed by their healthcare provider as SOC if PN is still required.

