Appendix 1 Schedule of Events Table

Evaluation	Evaluation Screening Baseline ^a Dai		Daily	Study Treatment Day (every 15 days ±2 days)					End of Study Treatment ^o
				15	30	45	60	75	or Day 90 (± 2 days)
Informed consent / assent (as applicable)	X								
Confirm eligibility	X								
Randomization ^b	Х								
Demographics ^c	Х								
Medical history including diagnosis for requiring PN	Х	Х							
Physical examination including length or height and head circumference	X	Х		X	X	X	Х	X	Х
Body weight ^d	Х	Х	Х	Х	Х	Х	Х	Х	Х
Vital signs ^e	Х	Х	Х	Х	Х	Х	Х	Х	Х
Diagnosis of neonatal morbidities ^f									Х
Laboratory Evaluations									
Hematology and serum chemistry	Х	Х	Standard-of-Care and every 15 days ± 2 days						
Triglyceride levels	X	Х	Standard-of-Care and every 15 days ±2 days						
Hepatic function tests	Х	Х	Stand	ard-o	f-Car	e and	ever	y 15 a	days ±2 days
Fatty acid profile and Holman Index ^g		Х		Х	Х	Х	Х	Х	Х
Genetic polymorphism sample (buccal swab) ^h		Х							
Phytosterol, cholesterol, and squalene levels ⁱ		Х		Х	Х	Х	х	Х	Х
Human chorionic gonadotropin (hCG) ^j	X								
Nutritional Intake									
PN lipid intake ^k		X	X	Х	Χ	Χ	Х	Х	X
Other macronutrient PN intake		Х	Х	Х	Х	Х	Х	Х	Х
Breast milk intake ¹	X	Х	Х	Х	Х	Х	Х	Х	Х
Enteral formula intake	X	Х	Х	Χ	Χ	Х	Χ	Х	X

Evaluation	Screening Baseline ^a		Daily	Study Treatment Day (every 15 days ±2 days)				End of Study Treatment ^o	
				15	30	45	60	75	or Day 90 (± 2 days)
Oral food intake	Х	Х	Х	Х	Х	Х	Х	Х	Х
Concomitant medications / nutritional supplements ^m	Х	Х	Х	Х	Х	Х	Х	Х	Х
Concomitant procedures	Х	Х	Х	Х	Х	Х	Х	Х	Х
Adverse events ⁿ	Х	Х	Х	Χ	Χ	X	Χ	Χ	Х

PN=parenteral nutrition

^a Baseline evaluations should be done \leq 24 hours before first study treatment administration, however, baseline laboratory assessments may be done within ±24 hours of first study treatment administration. Baseline tests need not be repeated if within 24 hours of screening sampling. Buccal swabs can be collected at any time before the end of study treatment.

^b Randomization is recommended within 24 hours of signing consent but must occur within 3 days of signing consent (section 7.1)

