2.1.1 Definition of baseline

Unless otherwise specified, baseline is defined as the values collected at the baseline visit. The value closest to the start of treatment will be used for baseline if multiple values (e.g. laboratory re-tests) are available. If the value at baseline is missing, then the value at the screening visit will be used as baseline.

Any medical condition that is present at the time that a participant is screened will be considered baseline medical history and will not be reported as an adverse event.

Change from baseline variables will be calculated as the post-treatment value minus the value at baseline.

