14.3.6.2.2	FAS	Shift Table of Hepatic Integrity for End of
		Treatment and Maximum Values
14.3.6.2.3	FAS	Hepatic Integrity: Days from Baseline to
		Maximum Value
14.3.6.3.1	FAS	Plasma Phytosterols, Cholesterol, and
		Squalene Levels
14.3.6.3.2	FAS	Plasma Phytosterols Correlation with Direct
		Bilirubin
14.3.6.4.1	FAS	Nutritional Intake from Parenteral Nutrition
14.3.6.4.2	FAS	Nutritional Intake from Enteral Nutrition
14.3.6.4.3	FAS	Nutritional Intake from IV Fluids
14.3.6.4.4	FAS	Overall Nutritional Intake
14.3.7.1	SS	Neonatal Morbidities at End of Treatment
14.3.8.1	SS	Vital Signs Summary and Change from
		Baseline
14.3.9.1	SS	Hematology Summary and Change from
		Baseline
14.3.9.2	SS	Liver Function Test Summary and Change
		from Baseline
14.3.9.3	SS	Serum Chemistry Summary and Change from
		Baseline

—

14.3.10	SS	Treatment Exposure
Listing Number	Analysis	Listing Name
	Population	
16.2.1	N/A	Patient Disposition
16.2.2	FAS	Protocol Deviations
16.2.3.1	N/A	Patients Excluded from Efficacy Analyses
16.2.4.1	FAS	Demographic and Baseline Characteristics
16.2.4.2.1	FAS	Medical History
16.2.4.2.2	FAS	Diagnosis for Parenteral Nutrition
16.2.4.3.1	FAS	Concomitant Medications for Patient
16.2.4.3.2	FAS	Concomitant Medications for Mother
16.2.4.4	FAS	Concomitant Procedures
16.2.5.1	SS	Treatment Exposure
16.2.6.1	FAS	Growth Parameters
16.2.7.1.1	SS	Pre-Treatment Adverse Events
16.2.7.1.2	SS	Treatment Emergent Adverse Events
16.2.7.1.3	SS	Serious Pre-Treatment Adverse Events
16.2.7.1.4	SS	Serious Treatment Emergent Adverse Events
16.2.7.1.5	SS	Treatment Emergent Adverse Events of
		Special Interest
16.2.7.1.6	SS	Treatment Emergent AEs related to study
		treatment
16.2.7.1.7	SS	Serious Treatment Emergent AEs related to
		study treatment
16.2.7.1.8	SS	Treatment Emergent AEs leading to
		withdrawal
16.2.7.1.9	SS	Treatment Emergent AEs leading to death
16.2.7.2.1	SS	Neonatal Morbidities
16.2.8.1.1	FAS	Holman Index Measurements
16.2.8.1.2	FAS	Fatty Acid Profile
16.2.8.1.3	FAS	Genetic Polymorphism
16.2.8.2.1	FAS	Parenteral Nutrition-Associated Liver Disease
		(PNALD) Values
16.2.8.2.2	FAS	Hepatic Integrity Values
16.2.8.2.3	FAS	Drug Induced Liver Injury
16.2.8.2.4	FAS	Plasma Phytosterols, Cholesterol, and
		Squalene Levels
16.2.8.3.1	SS	Hematology Laboratory Values
16.2.8.3.2	SS	Liver Function Test Values
16.2.8.3.3	SS	Serum Chemistry Values
16.2.9.1	SS	Vital Signs
16.2.10.1	SS	Physical Examinations
16.2.11.1.1	FAS	Parenteral Nutrition Intake

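### Neonatal morbidity status at end of treatment is reported as infants developing the morbidity, with no rule to separate disease present before the first study dose from new disease

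*SAP*

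**What the plan says.** **The summary.** SAP 2.5.2.1 opens with "Neonatal morbidities at the end of treatment are defined in the eCRF as" and then lists bronchopulmonary dysplasia (BPD), retinopathy of prematurity (ROP), intraventricular hemorrhage (IVH), periventricular leukomalacia (PVL), NEC and late-onset sepsis. Its next paragraph plans frequencies and percentages of preterm infants "developing neonatal morbidities will be summarized descriptively by treatment group". The output, Table 14.3.7.1 on the Safety Set, is titled "Neonatal Morbidities at End of Treatment". Protocol 9.6.3 asks only for n and percentage by treatment group; *developing* is the SAP's word.

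**Timing of collection.** In the protocol's Schedule of Events (Appendix 1), the row "Diagnosis of neonatal morbidities" has one mark, in the End of Study Treatment column. Protocol 7.2.4 agrees: "In addition, the following data will be collected at end of study treatment". Protocol 7.2.3, however, puts the same diagnoses under a different rule: "The following procedures will be performed at intervals determined by the SOC at each investigational site".

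**Entry.** Protocol 6.3 gives examples of diagnoses requiring PN at screening, among them "necrotizing enterocolitis; sepsis; short bowel syndrome". Protocol 4.3 does not exclude NEC. It mentions sepsis only as an example of severe unresponsive illness, judged by the investigator. Under Protocol 4.2, preterm infants may enter up to 1 month corrected age.

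**Conditions present at entry.** SAP 2.1.1 states: "Any medical condition that is present at the time that a participant is screened will be considered baseline medical history". The sentence goes on to keep such conditions out of adverse event (AE) reporting. SAP 2.5.1.1 divides AEs into pre-treatment and treatment-emergent by start date.

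**The concern.** Having a morbidity at the end of treatment and developing it on treatment are different quantities. The first includes disease that was there before the first study dose. The second needs an onset date, and a denominator limited to infants who did not yet have the disease. The SAP collects the first and names it as the second, and states no step that converts one into the other.

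An infant enrolled because NEC made PN necessary could thus appear in a safety table as having developed NEC on Clinolipid or Intralipid. The stated incidence would be too high in each arm. With few preterm infants, a chance difference in disease at entry could also be read as a drug effect. The same infant could be treated differently in two safety outputs: NEC present at screening stays out of the treatment-emergent AE tables but can be counted in Table 14.3.7.1.

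**Working it through.** The documents state no rate or calculation on this point, so there is no figure to reproduce. The sample size of 100 (50 per arm) rests on feasibility, and the number of preterm infants is not given.

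**Step 1. Can a listed morbidity precede the first study dose?**

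- NEC: yes. It is a named reason for PN at screening and is not an exclusion.
- Sepsis: possibly. The PN diagnosis is sepsis and the morbidity is late-onset sepsis, and some septic infants are screened out.
- BPD, ROP, IVH and PVL: not among the listed PN diagnoses, but the entry window allows them. An infant born at 24 weeks can enter up to 1 month corrected age. Even counting only to the 37-week limit for prematurity, that is 37 − 24 = 13 weeks plus one month after birth.

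**Step 2. Does the plan remove such cases?** SAP 2.5.2.1 has no onset rule, baseline exclusion or at-risk denominator. The Schedule of Events has no morbidity assessment at Screening or Baseline. SAP 2.1.1 removes conditions present at screening from AE reporting, not from this table. Nothing stated in either document removes them.

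**Step 3. How large could the effect be? (Assumed inputs.)** Let p0 be the share of infants with the morbidity before treatment and q the new-onset risk among the rest. If everyone with the morbidity at the end of treatment is counted, and pre-existing disease is still recorded then:

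reported proportion = p0 + (1 − p0) × q

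share of counted cases that were pre-existing = p0 / reported proportion

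| p0 | q | Reported | Share pre-existing |
|---|---|---|---|
| 5% | 5% | 0.05 + 0.95 × 0.05 = 9.8% | 51% |
| 5% | 10% | 0.05 + 0.95 × 0.10 = 14.5% | 34% |
| 10% | 5% | 0.10 + 0.90 × 0.05 = 14.5% | 69% |
| 10% | 10% | 0.10 + 0.90 × 0.10 = 19.0% | 53% |
| 20% | 5% | 0.20 + 0.80 × 0.05 = 24.0% | 83% |
| 20% | 10% | 0.20 + 0.80 × 0.10 = 28.0% | 71% |

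The table would show 9.8% to 28% where the new-onset risk is 5% to 10%. In counts, with 20 preterm infants per arm, p0 = 10% and q = 5%, the expected number is 20 × 0.10 = 2 pre-existing plus 20 × 0.90 × 0.05 = 0.9 new.

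**Step 4. Could chance unbalance the arms? (Assumed inputs.)** Treat the number of pre-existing cases in each arm as an independent binomial (n, p0). The probability that the arms differ by 3 or more cases is:

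| Preterm infants per arm | p0 = 5% | p0 = 10% | p0 = 20% |
|---|---|---|---|
| 20 | 6.7% | 18.0% | 32.0% |
| 30 | 13.1% | 27.5% | 41.7% |
| 40 | 19.0% | 34.6% | 48.3% |

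Randomization is stratified by site and age group, not by the diagnosis requiring PN, so the design does not specifically control this imbalance.

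**The case against.** The best defence is that this is an ambiguity, not a proven miscount. The SAP refers to the eCRF, which is not among the documents and may hold an onset date. Read literally, *developing* already excludes old disease. New NEC or sepsis reported as an AE also enters the treatment-emergent tables with its start date, and the listings of medical history, PN diagnosis and morbidities would let a reader trace prior cases. The table is descriptive, no test is planned, and disease that precedes randomized treatment is balanced in expectation.

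Much of this stands, and it limits the claim to what *can* be counted as new. It does not remove the point: the SAP uses no onset date for this table, and its definition and table title both describe status at end of treatment. The AE tables do not correct a separate planned table.

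A reader might infer four stronger things, which the documents do not support:

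- **That pre-existing disease will certainly be counted as new.** The SAP states no counting rule, and the form is not shown.
- **That the morbidities are recorded only once.** The Schedule of Events and Protocol 7.2.4 suggest so, but 7.2.3 also lists them at standard-of-care intervals.
- **That SAP 2.5.2.1 contradicts SAP 2.1.1.** The 2.1.1 rule is written for AE reporting. The morbidity table departs from the approach used for AEs; it does not break a stated rule.
- **That a treatment comparison is biased or a risk ratio diluted.** No risk ratio is planned. With an assumed 15% pre-existing and new onset of 5% versus 10% among the rest, the table would show 0.15 + 0.85 × 0.05 = 19.25% and 0.15 + 0.85 × 0.10 = 23.5%. The ratio falls from 2.0 to 1.22, but the difference only from 5 to 4.25 points. These rates have no source in the documents.

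**Conclusion.** The point holds in this form: the SAP labels an end-of-treatment status as on-treatment development, with nothing to separate prior from new disease in a population where prior disease is allowed. It is firm for NEC, weaker for sepsis, and for the other four morbidities rests on the entry window alone.

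The consequence is a possible overstatement of incidence in each arm, with no between-arm bias expected but some risk of chance imbalance. The illustrated sizes (about 10–28% shown against 5–10% new onset; a 7–48% chance of a difference of 3 or more pre-existing cases) depend on assumed values: 5–20% pre-existing, 5–10% new onset and 20–40 preterm infants per arm. Importance is moderate: this is one descriptive safety table, but in a vulnerable group, and the remedy is cheap.

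**What to change.** - **SAP 2.5.2.1 and Table 14.3.7.1:** for each morbidity, count as new only cases with onset on or after the first study dose, among infants free of that morbidity at baseline. Take baseline status from medical history and the diagnosis requiring PN, and onset from the recorded dates. Show pre-existing cases by arm in a separate row.
- **Fallback:** where prior status cannot be established from these sources, drop *developing* and label the result as prevalence at end of treatment.
- **Protocol 7.2.3, 7.2.4 and Schedule of Events:** reconcile whether the diagnoses are collected at standard-of-care intervals or at end of treatment only.

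The cost is a few sentences in the SAP, a revised table shell and a programmed check. Medical history and PN diagnosis (Protocol 6.3) and AE onset dates (Protocol 6.13.1) are already collected, so no new visit or assessment is needed. The split mirrors the one the SAP already applies to AEs.

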2.5.2.2 Derivation of Vital Signs

Vital signs including heart rate (beats/min), respiratory rate (breaths/min), systolic and diastolic blood pressure (mmHg), and body temperature (°C). are collected daily. Change from baseline will be calculated for all visits using the formula below:

Value post baseline - Value at baseline

2.5.2.3 Analysis of Vital Signs

Vital signs will be summarized descriptively using n, mean, standard deviation, minimum, median, and maximum for each visit. Change from baseline will also be summarized descriptively for all post-baseline visits.

2.5.2.4 Derivation of Laboratory Results

Laboratory testing (clinical parameters analyzed at local lab) is collected at baseline and then as per the SOC for each investigational site and on an approximately 15-day basis. Missingness in data is expected since laboratory parameters are collected per SOC and laboratory collection listed are optional.

Any quantitative laboratory parameters that are given as '<xx' or '>xx' in the database will be imputed with the absolute value of the number without the sign (e.g., <2.2 will be imputed as 2.2) for the calculation of the changes from baseline, the descriptive statistics, and shift tables.

2.5.2.5 Analysis of Laboratory Results

Laboratory parameters will be summarized descriptively using n, mean, standard deviation, minimum, median, and maximum at each visit. Change from baseline will also be provided for all cases where baseline assessments are available.

2.5.2.6 Derivation of Treatment Exposure

The following will be calculated to summarize treatment exposure:

Infusion duration (in hours/day):

End datetime of administration - Start datetime of administration

If multiple infusions were given each day, then the above will be done for each administration and summed together.

Administered Daily Infusion Rate (mL/kg/day):

Total Volume Administered on Day X (mL) Lipid dosing weight on Day X (kg)

Administered Daily Dose (g/kg/day):

 $\frac{Total Volume Administered on Day X (mL)}{Lipid dosing weight on Day X (kg)} * 0.2$

Administered Infusion Rate (g/kg/h):

Administered Daily Dose (g/kg/day) Infusion Duration (hr/day)

Total Study Treatment Days (days):

(End Date of Study Treatment - Start Date of Study Treatment) + 1

Total Pre-Study Treatment Days (days): a count of the number of days that prerandomization lipids were reported. If a patient had more than one infusion per day, then the sum of all infusions over that day should be used in the calculations above. For example, if there are two infusions of 200 mL each over 4 hours a piece, the total volume administered should be 400 mL and the total treatment duration should be 8 hours.

2.5.2.7 Analysis of Treatment Exposure

The above parameters, will be summarized by treatment group using n, mean, standard deviation, minimum, median, and maximum.

2.5.2.8 Physical Examinations

Results of physical examinations will be listed only.

2.5.3 Independent Data Safety Monitoring Board

There is a DSMB for this study that reviews data at four different time points in the study (10%, 50%, and 90% of enrollment). Refer to the DSMB Charter as well as the DSMB SAP for DSMB activities and analyses for the study.

2.6 Other general principles

2.6.1 Adjustment for covariates

There are no adjustments for covariates for any analyses in this study.

2.6.2 Handling of Dropouts or Missing data

All data collected up to the point where the patient drops out will be used for analyses.

Aside from missing weight in the calculation of nutritional intake, no missing data will be imputed for this study.

2.6.3 Multicenter Studies

This study was conducted in approximately 10 sites across the United States. Data from all sites will be pooled together for analyses.

2.6.4 Multiple Comparison/Multiplicity

No formal statistical tests are calculated for this study, so no multiplicity adjustments are needed.

2.6.5 Use of an "efficacy subset" of patients

A sensitivity analysis of the primary endpoint will be completed on the per protocol set. The PPS (as defined in section 1.5.1) is a subset of the full analysis set.

2.6.6 Rounding and Decimal Places

The estimated mean, Q1, median, and Q3 for a set of values will be displayed to 1 more significant digit than the original values, standard deviations will be displayed to 2 more significant digits, and minimum and maximum values will be displayed with the same number of significant digits as the original values. All percentages will be displayed out to 1 decimal place. For height, weight, and head circumference, up to 4 reported decimals are shown.

3. CHANGES FROM ANALYSIS PLANNED IN PROTOCOL

There are no planned changes in analyses from the protocol.

5. APPENDIX

5.1 Appendix 1: List of Tables, Listings, and Figures

Table Number	Analysis	Table Name
	Population	
14.1.1	N/A	Patient Overview
14.1.2	FAS	Patient Disposition
14.1.3	FAS	Protocol Deviations
14.1.4	FAS	Categorical Demographic and Baseline
		Characteristics
14.1.5	FAS	Continuous Demographic and Baseline
		Characteristics
14.1.6	FAS	Medical History by Coded Drug Term
14.1.7.1	FAS	Prior and Concomitant Medications by Coded
		Drug Term for Patient
14.1.7.2	FAS	Prior and Concomitant Medications by Coded
		Drug Term for Mother
14.2.1	FAS	Growth Parameters
14.3.1.1.1	SS	Summary of Adverse Events
14.3.1.1.2	SS	Treatment Emergent Adverse Events by
		Treatment, SOC, and Preferred Term
14.3.1.1.3	SS	Treatment Emergent Serious Adverse Events
14.3.1.1.4	SS	Treatment Emergent Adverse Events of
		Special Interest
14.3.1.1.5	SS	Treatment Emergent Adverse Events related
		to study treatment
14.3.1.1.6	SS	Treatment Emergent Serious Adverse Events
		related to study treatment
14.3.1.1.7	SS	Treatment Emergent Adverse Events leading
		to withdrawal
14.3.1.1.8	SS	Treatment Emergent Adverse Events leading
		to death
14.3.1.2.1	SS	Treatment Emergent Adverse Events in ≥5%
		of Patients by Treatment and Preferred Term
14.3.1.3.1	SS	Treatment Emergent Adverse Events by
		Treatment, SOC, Preferred Term, and
		Severity
14.3.1.3.2	SS	Serious Treatment Emergent Adverse Events
		by Treatment, SOC, Preferred Term, and
140100		Seventy
14.3.1.3.3	SS	Treatment Emergent Adverse Events by
		Treatment, SOC, Preferred Term, and
		Relationship to Study Treatment

—

14.3.1.3.4	SS	Serious Treatment Emergent Adverse Events
		by Treatment, SOC, Preferred Term, and
		Relationship to Study Treatment
14.3.4.1	SS	Listing of Abnormal Hematology Values
14.3.4.2	SS	Listing of Abnormal Liver Function Values
14.3.4.3	SS	Listing of Abnormal Serum Chemistry Values
14.3.4.4	SS	Listing of Abnormal Fatty Acid Profile
		Values
14.3.5.1.1	FAS	Primary Endpoint: Essential Fatty Acid
		Deficiency
14.3.5.1.2	PPS	Primary Endpoint: Essential Fatty Acid
		Deficiency
14.3.5.2.1	FAS	Primary Endpoint: Holman Index Values
14.3.5.2.2	PPS	Primary Endpoint: Holman Index Values
14.3.5.3.1	FAS	Primary Endpoint: Time to EFAD
14.3.5.3.2	PPS	Primary Endpoint: Time to EFAD
14.3.5.4.1	FAS	Fatty Acid Profile
14.3.5.4.2	PPS	Fatty Acid Profile
14.3.5.5.1	FAS	Genetic Polymorphism
14.3.5.5.2	PPS	Genetic Polymorphism
14.3.6.1.1	FAS	Parenteral Nutrition-Associated Liver Disease
14.3.6.2.1	FAS	Hepatic Integrity
14.3.6.2.2	FAS	Shift Table of Hepatic Integrity for End of
		Treatment and Maximum Values
14.3.6.2.3	FAS	Hepatic Integrity: Days from Baseline to
		Maximum Value
14.3.6.3.1	FAS	Plasma Phytosterols, Cholesterol, and
		Squalene Levels
14.3.6.3.2	FAS	Plasma Phytosterols Correlation with Direct
		Bilirubin
14.3.6.4.1	FAS	Nutritional Intake from Parenteral Nutrition
14.3.6.4.2	FAS	Nutritional Intake from Enteral Nutrition
14.3.6.4.3	FAS	Nutritional Intake from IV Fluids
14.3.6.4.4	FAS	Overall Nutritional Intake
14.3.7.1	SS	Neonatal Morbidities at End of Treatment
14.3.8.1	SS	Vital Signs Summary and Change from
		Baseline
14.3.9.1	SS	Hematology Summary and Change from
		Baseline
14.3.9.2	SS	Liver Function Test Summary and Change
		from Baseline
14.3.9.3	SS	Serum Chemistry Summary and Change from
		Baseline

—

14.3.10	SS	Treatment Exposure
Listing Number	Analysis	Listing Name
	Population	
16.2.1	N/A	Patient Disposition
16.2.2	FAS	Protocol Deviations
16.2.3.1	N/A	Patients Excluded from Efficacy Analyses
16.2.4.1	FAS	Demographic and Baseline Characteristics
16.2.4.2.1	FAS	Medical History
16.2.4.2.2	FAS	Diagnosis for Parenteral Nutrition
16.2.4.3.1	FAS	Concomitant Medications for Patient
16.2.4.3.2	FAS	Concomitant Medications for Mother
16.2.4.4	FAS	Concomitant Procedures
16.2.5.1	SS	Treatment Exposure
16.2.6.1	FAS	Growth Parameters
16.2.7.1.1	SS	Pre-Treatment Adverse Events
16.2.7.1.2	SS	Treatment Emergent Adverse Events
16.2.7.1.3	SS	Serious Pre-Treatment Adverse Events
16.2.7.1.4	SS	Serious Treatment Emergent Adverse Events
16.2.7.1.5	SS	Treatment Emergent Adverse Events of
		Special Interest
16.2.7.1.6	SS	Treatment Emergent AEs related to study
		treatment
16.2.7.1.7	SS	Serious Treatment Emergent AEs related to
		study treatment
16.2.7.1.8	SS	Treatment Emergent AEs leading to
		withdrawal
16.2.7.1.9	SS	Treatment Emergent AEs leading to death
16.2.7.2.1	SS	Neonatal Morbidities
16.2.8.1.1	FAS	Holman Index Measurements
16.2.8.1.2	FAS	Fatty Acid Profile
16.2.8.1.3	FAS	Genetic Polymorphism
16.2.8.2.1	FAS	Parenteral Nutrition-Associated Liver Disease
		(PNALD) Values
16.2.8.2.2	FAS	Hepatic Integrity Values
16.2.8.2.3	FAS	Drug Induced Liver Injury
16.2.8.2.4	FAS	Plasma Phytosterols, Cholesterol, and
		Squalene Levels
16.2.8.3.1	SS	Hematology Laboratory Values
16.2.8.3.2	SS	Liver Function Test Values
16.2.8.3.3	SS	Serum Chemistry Values
16.2.9.1	SS	Vital Signs
16.2.10.1	SS	Physical Examinations
16.2.11.1.1	FAS	Parenteral Nutrition Intake

16.2.11.1.2	FAS	Parenteral Nutrition Macronutrients
16.2.11.2.1	FAS	Enteral Nutrition Intake: Formula, Breast
		Milk, and Nutritional Shakes
16.2.11.2.2	FAS	Enteral Nutrition Intake: Additives and
		Fortifiers
16.2.11.2.3	FAS	Enteral Nutrition Intake: Oral Intake /
		Breastfeeding
16.2.11.2.4	FAS	Enteral Nutrition Macronutrients
16.2.11.3.1	FAS	IV Fluid Intake in addition to Parenteral
		Nutrition
16.2.11.3.2	FAS	IV Fluid Intake Macronutrients
16.2.11.4.1	FAS	Overall Nutritional Intake

Figure Number	Analysis	Figure Name
	Population	
14.2.1	FAS	Box Plots of Growth Parameters by
		Treatment Group
14.3.5.2.1	FAS	Holman Index over Time
14.3.5.2.2	PPS	Holman Index over Time
14.3.6.1.1	FAS	Direct Bilirubin over Time
14.3.6.1.2	PPS	Direct Bilirubin over Time
14.3.6.2.1	FAS	Assessment of Drug Induced Liver Injury:
		ALT
14.3.6.2.2	FAS	Assessment of Drug Induced Liver Injury:
		AST
14.3.6.2.3	FAS	Time Course of Hy's Law Cases
14.3.6.3.2	FAS	Scatterplots of Plasma Phytosterols vs. Direct
		Bilirubin
14.3.6.4.1.1	FAS	Box Plots of Ordered Parenteral Nutrition
		Intake by Treatment Group
14.3.6.4.1.2	FAS	Box Plots of Administered Parenteral
		Nutrition Intake by Treatment Group
14.3.6.4.2.1	FAS	Box Plots of Ordered Enteral Nutrition Intake
		by Treatment Group
14.3.6.4.2.2	FAS	Box Plots of Administered Enteral Nutrition
		Intake by Treatment Group
14.3.6.4.3	FAS	Box Plots of Administered IV Fluid Intake by
		Treatment Group
14.3.6.4.4.1	FAS	Box Plots of Overall Ordered Nutritional
		Intake by Treatment Group
14.3.6.4.4.2	FAS	Box Plots of Overall Administered Nutritional
		Intake by Treatment Group
